#### Secondary Effectiveness Hypothesis

The null and alternative hypotheses for the secondary effective analysis are:

$$H_{03e}: \mu_{t3e} - \mu_{c3e} \geq 0$$

$$H_{13e}: \mu_{t3e} - \mu_{c3e} < 0$$

Where  $\mu_{t3e}$  and  $\mu_{c3e}$  denote the population mean photopic monocular DCIVA (logMAR) at 66 cm in the first operative eyes at Month 6 (Visit 4) for the test and control IOLs, respectively.

#### Primary Safety Hypotheses

The null and alternative hypotheses for the first co-primary safety analysis are:

$$H_{01s}: p_{t1s} - p_{c1s} \geq 0.014$$

$H_{11s}$ :  $p_{t1s} - p_{c1s} < 0.014$

Where  $p_{t1s}$  and  $p_{c1s}$  denote the population proportion of first operative eyes at Month 12 (Visit 5) requiring secondary surgical intervention related to the optical properties of the IOL for the test and control IOLs, respectively.

## 9.2 SAMPLE SIZE DETERMINATION

As specified in ANSI Z80.12:2007 (R2017) –C.4, a minimum of 300 subjects implanted with the investigational IOL and 150 subjects implanted with the comparator IOL must be available for analysis at Visit 5 (postoperative days 330-420). To consider the potential loss of subjects between the time of enrollment and study completion, a total of approximately 501 subjects will be randomized and undergo surgery in this study. It is assumed that of approximately 501 subjects who undergo surgery, 51 subjects (10%) will be discontinued prematurely or lost to follow-up. Subjects will be randomized to receive either the investigational or comparator IOL in a 2:1 ratio. Of 501 subjects who undergo surgery, approximately 334 subjects will receive the investigational IOL and 167 subjects will receive the comparator IOL. Expecting a screen failure rate of 7%, up to 539 subjects will be enrolled in the study to have 501 subjects randomized and scheduled for surgery.

For effectiveness, 300 subjects (first operative eyes) randomized to FINEVISION HP IOL and 150 subjects (first operative eyes) randomized to AcrySof SN60AT [REDACTED] IOL completing through Month 6 (Visit 4) yields >99% power to reject  $H_{01e}$  in favor of  $H_{11e}$  and conclude the FINEVISION HP IOL is non-inferior to the AcrySof SN60AT [REDACTED] IOL in BCDVA (logMAR) at Month 6 (Visit 4), using a one-sided test with an alpha level of 0.05 and assuming no difference in mean BCDVA between test and control IOLs, a common standard deviation of 0.10 logMAR, and a non-inferiority margin of 0.10 logMAR.

Similarly with the sample size required for safety, 300 subjects (first operative eyes) randomized to FINEVISION HP IOL and 150 subjects (first operative eyes) randomized to AcrySof SN60AT [REDACTED] IOL completing through Month 6 (Visit 4) will have >99% power to demonstrate superiority of FINEVISION HP IOL to AcrySof SN60AT [REDACTED] IOL in DCIVA (reject  $H_{03e}$  in favor of  $H_{13e}$ ) and DCNVA (reject  $H_{02e}$  in favor of  $H_{12e}$ ) using a two-sided test with an alpha level of 0.05 and assuming a true difference in means of -0.10 logMAR (FINEVISION HP minus AcrySof SN60AT [REDACTED] with a common standard deviation of 0.14 logMAR.

For safety (based on ANSI Z80.12) 300 first operative eyes with FINEVISION HP IOL and 150 first operative eyes with AcrySof SN60AT [REDACTED] IOL completing through Month 12 (Visit 5) yields approximately 80% power to reject  $H_{01s}$  in favor of  $H_{11s}$  and conclude the FINEVISION HP IOL is non-inferior to the AcrySof SN60AT [REDACTED] IOL in secondary surgical interventions related to the optical properties of the IOL, using a one-sided Farrington-Manning score test with an alpha level of 0.05 and assuming the true proportion of secondary surgical interventions related to the optical properties of the FINEVISION HP IOL and of the AcrySof SN60AT [REDACTED] IOL is 0.001, and a non-inferiority margin of 0.014 (1.4%). Similarly, ISO 11979-7 specifies that a minimum of 300 subjects should complete a clinical evaluation of an IOL to obtain appropriate specificity around adverse event and visual acuity rates.

### 9.3 POPULATIONS FOR ANALYSES

#### Intent-to-Treat Set

The Intent-to-Treat (ITT) Set will include all randomized subjects (eyes).

#### All-Implanted Analysis Set

The All-Implanted Analysis Set will include all eyes with successful IOL implantation with a least 1 postoperative visit and will be the primary analysis for all effectiveness analysis.

#### Safety Set

The Safety Set will include all subjects with at least one eye implanted with a study lens.

#### Best Case Set

The Best Case Set will include subjects with all of the following characteristics:

- No major protocol deviations potentially affecting any of the primary effectiveness endpoints (BCDVA, DCNVA). Major protocol deviations that may potentially affect the primary effectiveness endpoints include, but are not limited to:
  - Inclusion of ineligible subjects
  - Implantation of incorrect IOL
  - Missed assessments for effectiveness endpoints at Month 6 (Visit 4)
  - Receipt of medication likely to interfere with visual performance at Month 6 (Visit 4)
- At least one eye implanted with a study lens
- No clinically significant preoperative ocular pathology in the first operative eye, including any of the following present prior to the operative visit
  - Pseudoexfoliation
  - Glaucoma
  - Uveitis
  - Retinal detachment
  - Diabetic retinopathy
  - Macular degeneration
  - Amblyopia
  - Other preoperative pathologies that are likely to affect central acuity
- No macular degeneration detected at any time in the first operative eye
- No previous surgery for the correction of refractive errors in the first operative eye

## 9.4 STATISTICAL ANALYSES

### 9.4.1 GENERAL APPROACH

Summaries for continuous variables will include the sample size, mean, standard deviation, median, minimum, and maximum. Summaries for discrete (categorical) variables will include the tabulation of frequencies and percentages.

The unit of analysis in this study will be the first operative eye for all primary effectiveness and safety summaries and will be the second operative eye and all eyes for supportive safety summaries; [REDACTED]

[REDACTED] Both eyes of each subject will be treated during the study. For those subjects whose eyes are both determined to be eligible for cataract surgery/IOL implantations at Preoperative Visit 0, the eye with the worse best-corrected distance visual acuity (BCDVA) will be scheduled for surgery first. If BCDVA is the same for both eyes, the right eye will be implanted first. Additionally, non-ocular AEs and medical history will be presented at the subject level.

### 9.4.2 HANDLING OF MISSING DATA

Missing data for primary and secondary efficacy analyses will be imputed under the following strategies.

Nonmonotone missing data will be multiply-imputed using treatment-based Markov Chain Monte Carlo (MCMC) methods; monotone missing data will be multiply imputed using regression methods assuming data as either missing at random or missing not at random as described below.

#### Primary Strategy

1. Withdrawal due to investigator's request: missing data assumed to be missing not at random. Control-based multiple imputations will be completed for superiority hypotheses and treatment-based multiple imputations will be completed for non-inferiority hypotheses. [hypothetical strategy]
2. Missing data without withdrawal or withdrawal due to reasons other than due to investigator's request: missing data assumed to be missing at random. Treatment-based multiple imputations will be completed. [hypothetical strategy]

#### Secondary Strategy

1. Withdrawal due to investigator's request: missing data assumed to be missing not at random. Control-based multiple imputations will be completed for superiority hypotheses and treatment-based multiple imputations, *using the worst half of the subjects who have data within the same treatment group*, will be completed for non-inferiority hypotheses. [hypothetical strategy]

2. Missing data without withdrawal or withdrawal due to reasons other than due to investigator's request: missing data assumed to be missing at random. Treatment-based multiple imputations will be completed. [hypothetical strategy]

---

#### 9.4.3 ANALYSIS OF PRIMARY EFFECTIVENESS ENDPOINTS

The statistical analyses described in ISO 11979-7, ISO 11979-9, and ANSI Z80.12 will be performed unless otherwise specified in the statistical analysis plan.

The co-primary effectiveness endpoints are:

- Photopic monocular logMAR best corrected distance visual acuity (BCDVA) in first operative eyes at Month 6 (Visit 4)
- Photopic monocular logMAR distance corrected near visual acuity (DCNVA) in first operative eyes at Month 6 (Visit 4)

Primary effectiveness endpoint analyses will be based on the All-implanted Analysis Set. Imputation of missing data will be performed utilizing multiple imputation techniques under assumptions of missing at random and missing not at random following the primary strategy presented in Section 9.4.2. As sensitivity analyses, the primary effectiveness analyses will be repeated using the secondary multiple imputation strategies presented in Section 9.4.2, as well as on the ITT and Best Case Sets using the primary multiple imputation strategy only. If the results of the ITT or Best Case Set robustness analyses materially differ from the primary analyses on the All-implanted Analysis Set then the results of investigations into the cause of such differences will be presented.

Photopic monocular BCDVA in first operative eyes at Postoperative Month 6 (Visit 4) will be primarily summarized using continuous summary statistics by treatment group. The treatment effect [mean Test group IOL visual acuity (VA) minus mean Control group IOL VA] in logMAR units will be presented in addition to a two-sided 90% t-distribution confidence interval around the difference. If the upper confidence limit is less than 0.1, then  $H_{01e}$  will be rejected in favor of  $H_{11e}$  and the FINEVISION HP IOL will be considered to be statistically non-inferior to the AcrySof SN60AT [REDACTED] IOL in BCDVA.

Photopic monocular DCNVA in first operative eyes at Postoperative Month 6 (Visit 4) will be summarized using continuous summary statistics in logMAR units by treatment group. The FINEVISION HP IOL will be compared to the AcrySof SN60AT [REDACTED] IOL using a two-sample t-test with a two-sided alpha of 0.05. If the two-sided p-value < 0.05 in favor of FINEVISION HP IOL for DCNVA, then the FINEVISION HP IOL will be considered to be statistically superior to the AcrySof SN60AT [REDACTED] IOL in DCNVA.

The study will be considered a success only if both primary effectiveness endpoints are met.

---

#### 9.4.4 ANALYSIS OF SECONDARY EFFECTIVENESS ENDPOINTS

The secondary effectiveness endpoint is:

- Photopic monocular logMAR DCIVA at 66 cm in first operative eyes at Month 6 (Visit 4)

The secondary effectiveness endpoint will be based on the All-implanted Analysis Set. Imputation of missing data and sensitivity analyses for the secondary effectiveness endpoint will be performed similarly as for the primary effectiveness endpoints.

Photopic DCIVA (66 cm) in first operative eyes at Postoperative Month 6 (Visit 4) will be summarized using continuous summary statistics in logMAR units by treatment group. The FINEVISION HP IOL will be compared to the AcrySof SN60AT [REDACTED] IOL using a two-sample t-test with a two-sided alpha of 0.05. If the two-sided p-value < 0.05 in favor of FINEVISION HP IOL for DCIVA, then the FINEVISION HP IOL will be considered to be statistically superior to the AcrySof SN60AT [REDACTED] IOL in DCIVA.

Inference will be conducted for the secondary effectiveness analysis only if all primary effectiveness endpoints are met.

#### 9.4.5 MULTIPLICITY CONSIDERATIONS

The Type I error rate for the primary effectiveness hypothesis tests will be controlled by requiring all primary effectiveness hypothesis test results to be statistically significant to declare success for the study. The overall Type I error rate including the primary and secondary effectiveness hypothesis tests will be controlled by a hierarchical testing strategy in which statistical inference for the secondary effectiveness endpoint will only be performed if the primary effectiveness analyses are successful.

#### 9.4.6 SAFETY ANALYSES

All safety analyses will be based on the Safety Set, unless otherwise specified.

##### **Co-primary Safety Analyses**

The co-primary safety endpoints are:

- Cumulative rate of SSIs related to the optical properties of the IOL in first operative eyes through Month 12 (Visit 5)
- Mean monocular distance contrast sensitivity (mesopic with and without glare at 1.5, 3, 6, and 12 cpd measured at 2.5m, and photopic with and without glare at 3, 6, 12, and 18 cpd, measured at 2.5m) in first operative eyes at Month 12 (Visit 5)

Descriptive statistics and analyses of co-primary safety variables will be based on first operative eyes and repeated as supportive analyses using second operative eyes as well as all operative eyes.

Secondary surgical interventions related to the optical properties of the IOL will be summarized by descriptive statistics for each IOL group. Noninferiority of FINEVISION HP IOL compared to AcrySof SN60AT [REDACTED] IOL in the proportions of first operative eyes with secondary surgical interventions related to the optical properties of the IOL will be evaluated using two-sided 90% Farrington method confidence intervals around the difference in proportions between the FINEVISION HP IOL and AcrySof SN60AT [REDACTED] IOL. If the upper limit of the confidence interval is less than 0.014, then  $H_{01s}$  will be rejected in favor of  $H_{11s}$  and the FINEVISION HP IOL will be considered statistically non-inferior to the

AcrySof SN60AT [REDACTED] IOL in rate of secondary surgical interventions related to optical properties of the IOL.

Monocular best-corrected distance contrast sensitivity (mesopic with and without glare at 1.5, 3, 6, and 12 cpd measured at 2.5m, and photopic with and without glare at 3, 6, 12, and 18 cpd, measured at 2.5m) in first operative eyes based on the Best Case Set will be summarized by descriptive statistics for each IOL group. The treatment group difference (mean Test group contrast sensitivity minus mean Control group contrast sensitivity) in log units will be presented by testing condition and frequency. Additionally, for each testing condition and frequency, the 5th percentile for the control group log contrast sensitivity will be determined and the percentage of subjects in the investigational arm who have achieved a log contrast sensitivity lower than this value will be reported.

### **Secondary Safety Analyses**

The secondary safety endpoints are:

- Rates of cumulative and persistent adverse events in first operative eyes through Month 12 (Visit 5), compared to the ISO SPE rates as described in ISO 11979-7
- Visual disturbances using the QoV questionnaire and QoV Supplemental Questions at Month 12 (Visit 5)

Descriptive statistics and analyses of secondary safety variables will be based on first operative eyes and repeated as supportive analyses using second operative eyes as well as all operative eyes.

Cumulative and persistent adverse events from ISO 11979-7 Table E.2 will be summarized using descriptive statistics by AE type and treatment and will be compared to the maximum number of cases allowed before the ISO SPE rate is exceeded.

Visual disturbances will be assessed by the QoV questionnaire with supplemental questions at Month 12 (Visit 5). Total QoV subscale scores (frequency, severity, bothersomeness) will be summarized using continuous summary statistics by treatment group. The frequencies and proportions of subjects for each response category for each question from the QoV Supplemental Questions will be presented by treatment group.

As additional categorical analyses of the QoV questionnaire, the frequencies and proportions of subjects for each response category of frequency, severity, or bothersomeness (separately) at Month 12 (Visit 5) will be presented for each item by treatment group. Subjects' satisfaction with the IOL at Month 12 (Visit 5) will also be summarized by treatment group.

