### 2.3 RISK/BENEFIT ASSESSMENT

#### 2.3.1 KNOWN POTENTIAL RISKS

Potential complications accompanying cataract or IOL implant surgery may include the following:

1. Ocular infection (endophthalmitis, microbial keratitis)
2. Inflammatory reaction [e.g. uveitis, Toxic anterior segment syndrome (TASS), hypopyon]
3. Anterior capsular phimosis
4. Corneal edema
5. Corneal endothelial damage
6. Cystoid macular edema (CME)
7. Secondary surgical intervention (including, but are not limited to: lens repositioning, lens replacement, vitreous aspiration, iridectomy for pupillary block, wound leak repair, and retinal detachment repair)
8. IOL dislocation, tilt, decentration, luxation, rotation
9. Elevated intraocular pressure
10. Pupillary block
11. Posterior capsular opacification (PCO)
12. Chromatic aberrations
13. Dysphotopsia
14. Loss of visual acuity
15. Deviation from target refraction
16. Hyphema
17. Retinal detachment

18. Iris or pupil damage
19. Posterior capsular rupture
20. Vitreous loss
21. Wound leak (positive Seidel)

In addition to these risks associated with cataract surgery and IOLs in general, multifocal IOLs in particular have been associated with an increased risk of reduced contrast sensitivity and also dysphotopias such as halos and glare, potentially leading to secondary surgical interventions.

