### 2.3.3 ASSESSMENT OF POTENTIAL RISKS AND BENEFITS

Based on a formal risk assessment, the benefit to risk profile is favorable as the benefits of improved intermediate and near vision are compared against the risks of reduced contrast sensitivity and visual disturbances, a known risk associated with multifocal IOLs.

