### **8.4 Data Analysis Conventions**

All data analysis will be performed by [REDACTED]. Statistical programming and analyses will be performed using SAS® version 9.4 or higher. Output will be provided in rich text format (RTF) for tables and portable document format (PDF) for tables, listings, and figures using landscape orientation.

Summaries for continuous and ordinal variables will include the number of observations (n), arithmetic mean, SD, median, minimum, and maximum. Minima and maxima will be reported with the same precision as the raw values; means and medians will be presented to one additional decimal place than reported in the raw values. Standard deviations will be presented to two additional decimal places than reported in the raw values. Summaries for discrete variables will include counts and percentages. All percentages will be rounded to one decimal place (i.e., XX.X%). Differences between test and control treatment groups will be calculated as test minus control and change from baseline will be calculated as follow-up visit minus baseline.

All statistical tests will be one-sided with a significance level of 0.05 ( $\alpha = 0.05$ ), except for the two superiority tests of DCIVA and DCNVA which will be two-sided with a significance level of 0.05. Correspondingly, confidence intervals (CI) for differences between treatment groups will be two-sided at 90% or 95% confidence. All p-values will be rounded to 4 decimal places; p-values less than 0.0001 will be presented as “<0.0001”; p-values greater than 0.9999 will be presented as “>0.9999.”

Unless otherwise specified, summaries will be presented by treatment group and, where appropriate, visit. Listings will be presented by subject number, treatment group, visit/time point, and parameter as applicable.

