- Severity: 0 (Not at all), 1 (Mild), 2 (Moderate), 3 (Severe)
- Bothersome: 0 (Not at all), 1 (A little), 2 (Quite), 3 (Very)

An example set of questions for the glare item/visual disturbance is provided below:

a) How often do you experience glare?  
Never    Occasionally    Quite often    Very often

b) How severe is the glare?  
Not at all    Mild    Moderate    Severe

c) How bothersome is the glare?  
Not at all    A little    Quite    Very

Scores for each subscale (frequency, severity, degree of bothersomeness) ranging from 0 to 100, with higher scores indicating a higher degree of visual disturbances, will be computed using a Rasch scoring algorithm which utilizes data from the original validation of the QoV.

The QoV Supplemental Questions will include the following questions:

1. How much trouble do you have with distance vision outdoors in daylight?
2. How much trouble do you have with distance vision outdoors at night or in dark situations?
3. How much trouble do you have with distance vision when indoors?
4. How much trouble do you have with near vision outdoors in daylight?
5. How much trouble do you have with near vision outdoors at night or in dark situations?
6. How much trouble do you have with near vision when indoors?
7. How much trouble do you have with blurred vision when looking at things in the distance?
8. How much trouble do you have with blurred vision when looking at things that are near?
9. How much trouble do you have with night vision?
10. How much trouble do you have with night driving?
11. How much trouble do you have with color disturbances?
12. If given the opportunity, would you again elect to be implanted with the same intraocular lens (IOL)?

The response options for questions 1 to 11 from the QoV Supplemental Questions will be "none," "a little," or "a lot." For question 12 regarding satisfaction with the IOL, responses of "yes" or "no" will be recorded.

The QoV Rasch subscale scores (frequency, severity, bothersomeness) will be summarized by treatment group using continuous summary statistics. As additional analyses of the QoV questionnaire, the categorical responses for each item at Month 12 (Visit 5) will be summarized by treatment group using discrete summary statistics.

The categorical responses from the QoV Supplemental Questions at Month 12 (Visit 5), including subjects' satisfaction with the IOL, will be summarized by treatment group using discrete summary statistics.

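### No between-arm difference or interval is planned for visual disturbance (QoV at Month 12), a secondary safety endpoint and a named risk of multifocal lenses

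*Protocol*

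**What the plan says.** Visual disturbance measured by the QoV questionnaire and its supplemental questions at Month 12 is a secondary safety endpoint in both documents (Protocol 3.2 and 9.4.6; SAP 3.2.2 and 15.2).

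- **Why it is measured.** Protocol 2.3.1 links multifocal lenses in particular with "dysphotopias such as halos and glare, potentially leading to secondary surgical interventions". Protocol 2.3.3 rests the benefit-risk assessment on a balance in which "the benefits of improved intermediate and near vision are compared against the risks of reduced contrast sensitivity and visual disturbances".
- **Planned analysis of the scores.** Protocol 9.4.6: "Total QoV subscale scores (frequency, severity, bothersomeness) will be summarized using continuous summary statistics by treatment group". SAP 15.2: "The QoV Rasch subscale scores (frequency, severity, bothersomeness) will be summarized by treatment group using continuous summary statistics".
- **Planned analysis of the items.** SAP 15.2: "the categorical responses for each item at Month 12 (Visit 5) will be summarized by treatment group using discrete summary statistics". The supplemental questions are treated in the same way, and the site and pupil-size analyses of QoV only repeat these summaries.
- **What a summary contains.** SAP 8.4: "Summaries for continuous and ordinal variables will include the number of observations (n), arithmetic mean, SD, median, minimum, and maximum".
- **General conventions.** SAP 8.4 also states "Differences between test and control treatment groups will be calculated as test minus control" and, following on from its sentence about hypothesis tests, "confidence intervals (CI) for differences between treatment groups will be two-sided at 90% or 95% confidence".
- **Baseline.** The Schedule of Activities places the patient-reported questionnaires, which include the QoV, at Visit 0 as well as at Visits 4 and 5. No planned analysis uses the Visit 0 QoV score.

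**The concern.** The benefit side of the balance is estimated as a randomised comparison: near and intermediate acuity each have a between-arm test. For visual disturbance, the reader gets two columns of arm summaries. A trial with a randomised control arm can say how large the excess of disturbance is and how precisely it is known. The visible plan does not commit to saying either.

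If the estimate is not specified in advance, someone will probably form it after unmasking. The choice of adjustment, of items, of response cut-point and of interval method would then be made with the results in view. A baseline- or site-adjusted estimate cannot be recovered from arm summaries at all.

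**Working it through.** **1. Which endpoints have a planned comparative statistic?**

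| Endpoint | Planned comparison | Where |
|---|---|---|
| BCDVA | difference, 90% CI | Protocol 9.4.3; SAP 13.1 |
| DCNVA, DCIVA | two-sided t-test | Protocol 9.4.3, 9.4.4; SAP 13.1, 13.2 |
| SSI related to optical properties | difference, 90% CI, margin 0.014 | Protocol 9.4.6; SAP 15.1 |
| Contrast sensitivity | mean difference, no CI stated | Protocol 9.4.6; SAP 15.1 |
| Cumulative and persistent AEs | exact binomial test against ISO rates | SAP 15.2 |
| QoV | none; summaries by arm | Protocol 9.4.6; SAP 15.2 |

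The SAP 8.4 conventions do not fill the last row. One fixes the direction of any difference that is calculated. The other sets the confidence level that corresponds to the tests, and QoV has no test.

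**2. The plan's own figure on the same sample.** The documents give no power or precision figure for QoV. The nearest is power above 99% for DCNVA with 300 and 150 completers, a difference of 0.10 logMAR, an SD of 0.14 and two-sided alpha of 0.05.

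- sqrt(1/300 + 1/150) = 0.10
- noncentrality = 0.10 / (0.14 × 0.10) = 7.14, against a critical t(0.975, 448) of 1.965
- power is above 99.99%, which agrees with the stated figure

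**3. Precision for a QoV subscale difference.** Inputs: 300 and 150 subjects at Month 12 (SAP 5) and a 0 to 100 scale (SAP 15.2). The SD is not in the documents, so a range is assumed.

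Half-width of the 95% CI = t(0.975, 448) × SD × sqrt(1/300 + 1/150) = 1.965 × 0.10 × SD = 0.197 SD

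| Assumed SD | 95% half-width (points) |
|---|---|
| 10 | 2.0 |
| 15 | 2.9 |
| 20 | 3.9 |
| 25 | 4.9 |

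**4. Gain from the Visit 0 score.** The standard error shrinks by sqrt(1 − r²). For assumed correlations between Visit 0 and Month 12:

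- r = 0.2: sqrt(0.96) = 0.98, a narrowing of 2%
- r = 0.4: sqrt(0.84) = 0.92, a narrowing of 8%

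**5. An item-level illustration.** Suppose 24 of 300 test subjects (8%) and 3 of 150 controls (2%) rate a symptom quite or very bothersome; both rates are assumed. The difference is 6.0 percentage points. The Miettinen-Nurminen 95% CI is about 1.7 to 10.0. A Wald interval gives 6.0 ± 1.96 × sqrt(0.08 × 0.92/300 + 0.02 × 0.98/150) = 6.0 ± 3.8, or 2.2 to 9.8. With only three control events the score-based interval is the safer choice.

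**The case against.** A reader might infer that the harm side of the benefit-risk comparison is never estimated. The documents do not support that. Protocol 2.3.3 names two risks, and one of them, contrast sensitivity, has a planned test-minus-control difference. SSIs related to optical properties, which Protocol 8.6 defines by intolerance of visual symptoms, have a difference with a 90% interval, so the severe end of visual disturbance is formally compared. Only the QoV part lacks an estimate. The SSI comparison does not stand in for it: at the planning rate of 0.001, 300 test eyes give 0.3 expected events, which says little about disturbances that patients live with. Glare and halos may also be reported as adverse events, but Protocol 9.4.6 compares those between arms only descriptively.

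A reader might also infer that the size and precision of an excess would be hidden. That is too strong. The planned n, mean and SD per arm, or the counts for items, determine an unadjusted difference and its interval. What cannot be recovered is the adjusted estimate and the assurance that the choices were made beforehand.

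Two further points stand. The QoV objective is only to evaluate visual disturbances and no hypothesis is attached to it, so descriptive reporting contradicts nothing in either document. And the SAP table list is not shown and some sections are redacted, so a difference column in a table shell cannot be ruled out.

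**Conclusion.** The point holds in a limited form. On the visible text, QoV at Month 12 is the only primary or secondary endpoint without any planned comparative statistic, and its Visit 0 score is collected but unused. The trial's validity and its success criteria are unaffected; the loss is a pre-specified estimate of a harm that the protocol itself weighs against the benefit.

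The planned sample would give a usable interval with no added subjects: a half-width of 0.197 SD, or 2.0 to 4.9 points for assumed SDs of 10 to 25. Baseline adjustment adds only 2% to 8% (assumed correlations 0.2 to 0.4), so the main gain is the stated difference and interval. The SDs, correlations and item rates are illustrations, because the documents give none.

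**What to change.** In SAP 15.2, add for each of the three Month 12 Rasch subscale scores the test-minus-control difference with a two-sided 95% CI, from a linear model with treatment, Visit 0 subscale score and site (the randomisation stratum).

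Optionally, for each of the 10 symptoms, add the between-arm difference in the percentage answering quite or very bothersome, with a 95% Miettinen-Nurminen CI. That cut-point is a proposal that the documents do not contain, and it should be fixed before unmasking.

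Label all of these as descriptive and unadjusted for multiplicity, with no alpha spent and no success rule. The cost is SAP wording and one extra table. The downsides are several unadjusted intervals that call for cautious reading, and that any excess of disturbances in the test arm will be shown explicitly.
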